19.3. Endpoints

19.3.1. Primary Efficacy Endpoint

The primary efficacy endpoint will be the response rate on EDSS and 90% confidence interval (CI) on Day 42 for each treatment group.

19.3.2. Primary Safety Endpoint

The primary safety endpoint will be a summary of general safety profile, including adverse events (serious and nonserious), vital signs and laboratory assessments by study period and over the entire study.

19.3.3. Secondary Efficacy Endpoints

- The response rates on MSIS-29 and 90% CIs on Day 7, Day 14, Day 21 and Day 42 for each treatment group.
- The response rates on EDSS and 90% CIs on Day 7 and Day 21 for each treatment group.
- CGI-I mean scores and 90% CIs on Day 7, Day 21 and Day 42 for each treatment group.

19.3.4. Exploratory Endpoints

- [REDACTED]
- [REDACTED]
- [REDACTED]
- [REDACTED]

19.4. Subject Characteristics

19.4.1. Demographics

The demographic information will be summarized for each analysis population by treatment group.

19.4.2. Medical and Surgical History

Relevant prior medical conditions or procedures will be summarized by body system and treatment group.

19.4.3. Prior and Concomitant Medications

Prior and concomitant medications will be coded according to the WHO Drug Dictionary. The incidence (number and percent) of prior and concomitant medication use will be summarized by treatment group.

19.4.4. Subject Disposition and Exposure to Study Drug

Subject disposition will be summarized for all randomized subjects. The number of subjects who complete the study and who do not complete the study along with the reasons for discontinuation from the study will be summarized.

19.5. Efficacy Analysis

A responder on EDSS is defined as a subject who achieves the following:

- ≥ 1.0 point improvement on EDSS score compared to baseline if baseline EDSS score was ≤ 5.5 .
- ≥ 0.5 point improvement on EDSS score if the baseline EDSS score was > 5.5 .

A responder on MSIS-29 is defined as a patient who achieves ≥ 8 point improvement on the physical subscale score of MSIS-29 compared to baseline.

Baseline is defined as the value observed prior to first dose of the study drug (Day 1).

The primary efficacy endpoint, the response rate on EDSS at Day 42, will be calculated by treatment group. Response rates and 90% Wilson CIs will be reported for each treatment group. These analyses will be performed for the mITT and Per-Protocol populations.

Summary statistics (n, mean, SD, median, minimum, and maximum) of the baseline value, the value at each scheduled postbaseline evaluation and the corresponding change from baseline for EDSS score will be presented by treatment group for all subjects in the mITT population and the Per-Protocol population.

A subject-by-subject data listing sorted by treatment group and subsequently by subject will be generated for all subjects in the mITT population.

For the secondary endpoints, the response rate endpoints will be analyzed and presented with the same approach as described above for the primary efficacy endpoint. The mean score endpoint will be calculated by treatment group. Mean, SD, and 90% CI will be presented by treatment group. All secondary efficacy analyses will use the mITT population.

For the exploratory endpoints, scores change from baseline will be calculated by treatment group. Mean, SD, and 90% CI will be presented by treatment group. All exploratory efficacy analyses will use the mITT population.

For all efficacy endpoints, the normality assumption of the data will be examined using appropriate normality test. If the test result shows the data is not normally distributed, then median, 10% and 90% percentiles will be presented instead of mean, SD and 90% CI.

The statistical analysis plan will describe in further detail the analyses for primary, secondary, and exploratory efficacy endpoints.

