13.1. Prohibited Concomitant Medications/Nondrug Therapies

The following medications/nondrug therapies are not permitted during the study from the Screening Visit through Day 42:

- Oral corticosteroids (prednisone/prednisone equivalent) in excess of the 3 to 5 days (given over a period of up to 7 days) of high dose treatment that is allowed during the screening period.
- Parenteral corticosteroids.
- Daclizumab, or any immunosuppressant (including but not limited to cyclophosphamide, mitoxantrone, or rituximab).
- Natalizumab (unless the subject is currently negative for JC virus based on a negative JC virus test in the 6 months prior to the first dose of Acthar).
- Live or live-attenuated vaccines.
- Intravenous immunoglobulin (IVIg).
- Any investigational drug, device, or procedure administered as part of a research study.

If any prohibited medication is taken during the study, all pertinent information will be recorded in source documents and the electronic case report form (eCRF). The designated study medical monitor (MM) must be informed immediately so the sponsor may determine whether to continue the subject in the study.

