15.3.1. Treatment Discontinuation

Treatment with study drug should be discontinued if any of the following occur:

- Development of accelerated hypertension (defined as systolic blood pressure \geq 180 *and* diastolic blood pressure \geq 100 mm Hg) that cannot be managed by the adjustment of concomitant medications such as antihypertensive medications.
- Development of congestive heart failure that cannot be managed by the adjustment of concomitant medications such as diuretics and antihypertensive medications.
- Development of diabetic signs/symptoms (ie, HbA1c $>$ 6.5%, or fasting plasma glucose $>$ 126 mg/dL, or classic symptoms of hyperglycemia with random plasma glucose $>$ 200 mg/dL).
- Subjects who undergo plasma exchange or IVIg due to lack of efficacy will be considered treatment failures and will be withdrawn from the study.
- Development of any other AE of at least moderate intensity and possibly, probably or definitely related to study drug that cannot be managed by the adjustment of concomitant medications.

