19.10. Missing Data

Given the mITT design, an imputation or some other procedure for handling missing primary endpoints is required.

For the primary efficacy endpoint, subjects who do not provide data to allow classification as responders will be considered nonresponders, that is, missing data will be imputed as “nonresponder”. A similar approach will be applied to secondary efficacy endpoints that are proportions.

For continuous secondary efficacy endpoints collected directly from the CRF, the method of last observation carried forward (LOCF) will be used to impute the missing values. For other continuous secondary efficacy endpoints that need to be derived based on patients’ response to a questionnaire, if the responses to an entire questionnaire are missing, LOCF will be applied; otherwise, the method of handling missing response is described in each individual section for the secondary efficacy endpoint analysis.

A full description of missing data imputation method for all endpoints will be described in the statistical analysis plan.

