21. SUBJECT DISCONTINUATION OR WITHDRAWAL

21.1. Subject Withdrawal

Subjects who discontinue, or are withdrawn from the study for any reason, will be required to enter the follow-up period and have the Early Termination and Follow-up safety assessments (see [Section 14.5](#) and [Section 14.6](#)) to assess their continued well-being.

The reason for discontinuation will be recorded. A subject may be discontinued from the study for the following medical or administrative reasons:

Withdrawal by Subject

Subjects will be free to discontinue from the study at any time. Subjects who have received at least 1 dose of study drug but do not complete the study will not be replaced.

Lack of Efficacy

Subjects who undergo plasma exchange or receive IVIg following treatment with Acthar due to lack of efficacy will be considered treatment failures and will be withdrawn from the study.

Adverse Event

If a dosed subject suffers an AE that, in the judgment of the investigator, sponsor or MM, presents an unacceptable consequence or risk to the subject, the subject will be discontinued from further participation in the study.

Death

In the event that a subject dies during the study, death will be the reason for discontinuation.

Lost to Follow-up

Every effort should be used to maintain contact with subjects during their participation in the study. A subject may be considered lost to follow up if there is no response to 3 attempts to reach the subject by telephone and no response to a certified letter sent to the last known address of the subject. Efforts to contact the subject should be noted in source documentation.

Met Withdrawal Criteria

If a subject develops a condition that meets any of the exclusion criteria ([Section 12.2](#)) or fails to meet an inclusion criteria ([Section 12.1](#)) during the study that is not considered to be an AE or is noncompliant (eg, has a positive pregnancy during the screening or treatment periods or positive drug screening test), the subject will be discontinued from further participation in the study. Discontinuation is also mandated for safety and/or tolerability issues as outlined in [Section 15.3.1](#).

Other

If the above reasons are not applicable, please use the “Other” option and provide the appropriate reason for subject withdrawal.

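### Section 19.5 scores EDSS response on score change alone, so a subject continued after prohibited corticosteroids who then improves counts as a Day 42 responder in the primary mITT analysis

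*Combined protocol and SAP*

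**What the plan says.** **Responder rule.** Section 19.5, repeated in the synopsis, opens with "A responder on EDSS is defined as a subject who achieves the following". Two thresholds follow: at least 1.0 point of improvement if baseline EDSS is 5.5 or below, and at least 0.5 if it is above 5.5. Treatment received in between is not mentioned.

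**Prohibited corticosteroids.** From screening through Day 42, section 13.1 bars "Oral corticosteroids (prednisone/prednisone equivalent) in excess of the 3 to 5 days" of the screening course, and bars parenteral corticosteroids. After a breach, "If any prohibited medication is taken during the study, all pertinent information will be recorded in source documents" and the eCRF, and "The designated study medical monitor (MM) must be informed immediately so the sponsor may determine whether to continue the subject in the study". No effect on responder status is stated.

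**Missing data.** Under 19.10, "subjects who do not provide data to allow classification as responders will be considered nonresponders". The rule is triggered by missing data only.

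**Population.** The mITT definition in 19.2 needs one dose and one postbaseline EDSS. It does not remove users of prohibited medication. Section 19.9 names mITT as the population for the primary analysis.

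**Treatment failures.** Section 15.3.1: "Subjects who undergo plasma exchange or IVIg due to lack of efficacy will be considered treatment failures and will be withdrawn from the study". Section 21.1: "Subjects who undergo plasma exchange or receive IVIg following treatment with Acthar due to lack of efficacy will be considered treatment failures". Neither lists corticosteroids. Section 21.1 also says that withdrawn subjects "will be required to enter the follow-up period and have the Early Termination and Follow-up safety assessments", and refers for these to 14.5 and 14.6. Under its withdrawal criteria it separately says that a noncompliant subject will be discontinued.

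**The concern.** Subjects are randomized because one high-dose corticosteroid course did not produce the required improvement. Study drug stops at Day 14 and the endpoint is at Day 42. That leaves four weeks in which a further corticosteroid course is possible. If one is given, the subject is kept in the study and the EDSS improves, the responder count cannot separate that improvement from an effect of study drug.

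The pilot makes no between-arm test. Section 9.1 says its purpose is to generate response rates from which a larger study can be sized. What such a rate represents therefore matters more here than it would in a trial where the rate was a secondary description. The protocol also labels one group of subjects treatment failures without saying that a treatment failure is a nonresponder.

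**Working it through.** **Step 1. Follow one subject through the text.** Take a subject who receives study drug, takes a prohibited corticosteroid after Day 14, is continued by the sponsor under 13.1, and at Day 42 is 1.0 point better from a baseline EDSS of 4.0.

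- 19.2: in mITT (dosed, with a postbaseline EDSS).
- 19.10: not imputed, because the classifying data exist.
- 15.3.1 and 21.1: not a treatment failure, because corticosteroids are not listed.
- 12.2, exclusion 7: does not apply, because it covers dosing during screening.
- 19.5: threshold met, so the subject is a responder.

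**Step 2. Set 13.1 beside 21.1.** Section 13.1 leaves continuation to the sponsor. Section 21.1 says a noncompliant subject will be discontinued, which can be read to include use of a prohibited drug. The documents do not say which governs.

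**Step 3. Plasma exchange or IVIg for lack of efficacy.** The subject is withdrawn as a treatment failure. Sections 14.5 and 14.6, to which 21.1 refers, both list FSS and EDSS, and 14.6 applies at Day 42 or at early termination. An EDSS taken after that therapy may therefore exist. No text says whether it counts as the Day 42 value, or that the failure status overrides it.

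**Step 4. Reproduce the plan's intervals (19.9).** Inputs: n = 30 per arm, 90% Wilson, z = 1.645, z² = 2.706.

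Centre = (p + z²/2n) / (1 + z²/n); half-width = z·√(p(1−p)/n + z²/4n²) / (1 + z²/n).

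- Acthar, 18/30: centre (0.6 + 0.0451)/1.0902 = 0.592; half-width 1.645 × √(0.0080 + 0.00075)/1.0902 = 0.141. Interval 45.1% to 73.3%, as stated.
- Placebo, 8/30: centre (0.2667 + 0.0451)/1.0902 = 0.286; half-width 1.645 × √(0.00652 + 0.00075)/1.0902 = 0.129. Interval 15.7% to 41.5%, as stated. The plan's 25% was evidently taken as 8/30 = 26.7%.

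**Step 5. Size per subject.** 1/30 = 3.3 points; 3.33/14.1 = 0.24 and 3.33/12.9 = 0.26, about a quarter of the stated precision. The documents give no rate of prohibited corticosteroid use, so k, the number of responders reclassified in an arm, is an assumption:

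| k | Acthar (90% Wilson) | Placebo (90% Wilson) |
|---|---|---|
| 0 | 18/30 = 60.0% (45.1–73.3) | 8/30 = 26.7% (15.7–41.5) |
| 1 | 17/30 = 56.7% (41.9–70.4) | 7/30 = 23.3% (13.2–37.9) |
| 2 | 16/30 = 53.3% (38.7–67.4) | 6/30 = 20.0% (10.7–34.3) |
| 3 | 15/30 = 50.0% (35.6–64.4) | 5/30 = 16.7% (8.4–30.5) |
| 5 | 13/30 = 43.3% (29.6–58.1) | 3/30 = 10.0% (4.1–22.6) |

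**Step 6. Effect on sizing a later study.** Assumed, not in the documents: two-sided 5%, 80% power.

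n per arm = [1.960·√(2p̄(1−p̄)) + 0.842·√(p₁(1−p₁) + p₂(1−p₂))]² / (p₁ − p₂)², with p̄ = (p₁ + p₂)/2.

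- 18/30 v 8/30: 33.49, so 34
- 17/30 v 8/30 (one in Acthar only): 41.19, so 42
- 18/30 v 7/30 (one in placebo only): 27.17, so 28
- 17/30 v 7/30 (one in each): 32.70, so 33
- 60% v the stated 25%: 30.11, so 31

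One in each arm changes n by 1. That is less than the change of 3 from using 25% instead of 8/30. Uneven use is what matters for sizing.

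**The case against.** **The rule is determinate and legitimate.** Scoring the observed EDSS whatever else was given is a recognised strategy, and 19.5 read literally does that. This stands: the plan is not silent. What is missing is a statement that the strategy was chosen, and a view of the alternative.

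**Other outputs expose the problem.** Prohibited medication is recorded and escalated, concomitant medication is summarised by arm (19.4.3), mITT subjects are listed individually, and the primary endpoint is repeated in the Per-Protocol population. All true, but none changes the primary mITT rate, and 19.2 does not define what completing as per protocol means.

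**Continued users may be rare.** If 21.1 is read to discontinue them, they are exceptions. That limits the size, and it is also why 13.1 and 21.1 need reconciling.

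**Detail is deferred.** Sections 19.1, 19.5 and 19.10 point to a separate SAP that is not among the documents. It may contain the rule, and the conclusion is limited accordingly.

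**Treating these subjects as nonresponders goes beyond the text.** This also stands. The treatment-failure wording covers plasma exchange or IVIg for lack of efficacy only. A reader might infer that the protocol already means corticosteroid users to fail, but nothing says so. A rule covering every corticosteroid for any reason could also fail a subject who had met the threshold by Day 21 and then took one dose for an unrelated condition.

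**Conclusion.** The point holds for subjects who are continued under 13.1: on the supplied text their improvement after prohibited corticosteroids counts as a primary response. The unlinked treatment-failure status is a second, smaller gap.

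The size is 3.3 points per subject at 30 per arm. It rests on an assumed number of such subjects, because the documents give none. Priority is low to moderate.

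Two stronger readings should be resisted. A reader might infer that the estimated difference is biased in a particular direction; that depends on which arm has more such use, which the documents do not say. A reader might also infer that missing data makes plasma exchange and IVIg recipients nonresponders in any case, since 21.1 speaks of safety assessments. Its reference to 14.5 and 14.6, which schedule EDSS, means this cannot be relied on.

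**What to change.** In 19.5 and 19.10, the synopsis and the separate SAP, state that in both arms:

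- (a) a subject declared a treatment failure under 15.3.1 or 21.1 is an EDSS nonresponder, whatever EDSS is later observed;
- (b) a subject who received corticosteroids prohibited by 13.1 for MS symptoms or relapse, between the first study-drug dose and the Day 42 EDSS, is a nonresponder in the primary analysis.

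Present (b) as a pre-specified analysis choice, not as the documents' own intent. Report two sensitivity analyses: one scoring observed Day 42 EDSS regardless of such treatment, and one counting any prohibited oral or parenteral corticosteroid, whatever the indication, as nonresponse.

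Reconcile the sponsor's discretion in 13.1 with the discontinuation of noncompliant subjects in 21.1. Align the treatment-failure wording too: 21.1 speaks of Acthar while 15.3.1 is not limited by arm. This is probably editorial, since 15.3 also uses the product name for study drug.

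The cost is a few sentences, flags derived from data already recorded (indication is collected under section 13) and two extra tables. The downside is that response rates may be slightly lower. The change concerns endpoint classification only and proposes nothing about patient care.

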16.3. Clinical Global Impression of Improvement

The CGI-I was developed for use in clinical research to provide a brief overview of the change in a subject's global function compared to baseline and regardless of study drug treatment (Guy, 1976; Busner and Targum, 2007). It requires a rating from 1 (very much improved) to 7 (very much worse).

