19. STATISTICAL METHODS AND PLANNED ANALYSIS

19.1. General Considerations

This section provides a general description of the statistical methods to be used in analyzing both safety and efficacy data. The key statistical issues or considerations will be addressed. A more detailed statistical analysis plan will be provided in a separate document that will be finalized prior to database lock.

Summary statistics will be provided for all study variables with descriptive statistics (number of observations, mean, SD, median, minimum, and maximum) for numerical (or continuous) variables. Frequency and percentages will be calculated for categorical variables. Data summary and analyses will be performed with SAS 9.2 or higher.

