19.7. Quality of Life/ Health Outcomes Analysis

The change from baseline in [REDACTED] will be summarized with mean change, SD, and 90% CI.

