19.9. Statistical Power and Sample Size Considerations

It is expected that 66 subjects will be randomized into 1 of 2 treatment groups: 80 U (1 mL) of Acthar per day for 14 consecutive days or placebo (1 mL) per day for 14 consecutive days in a 1:1 ratio (33 per group). The primary analysis is to generate point estimates and associated 90% CIs for the response rates on EDSS in the Acthar group and the placebo group at Day 42, respectively using a mITT analysis population. Assuming 3 subjects will not qualify for the mITT analysis population after randomization in each treatment group, there will be 30 mITT subjects in each group. Based on an expected 60% response rate in the Acthar group, the study can build a 90% Wilson CI of (45.1%, 73.3%) with approximate precision of 14.1%. Based on an expected 25% response rate in the placebo group, the study can build an approximate 90% Wilson CI of (15.7%, 41.5%) with approximate precision of 12.9%.

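### An unnamed normality test can remove the CGI-I mean and 90% CI that Section 19.3.3 defines as a secondary endpoint, and puts no interval estimate in their place

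*Combined protocol and SAP*

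**What the plan says.** Section 19.3.3 lists as a secondary efficacy endpoint: "CGI-I mean scores and 90% CIs on Day 7, Day 21 and Day 42 for each treatment group". It is the only secondary endpoint that is a mean; the others are responder rates.

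Section 19.5 first agrees: "The mean score endpoint will be calculated by treatment group. Mean, SD, and 90% CI will be presented by treatment group". Later in the same section, for all efficacy endpoints, "the normality assumption of the data will be examined using appropriate normality test", and if the data are judged non-normal, "then median, 10% and 90% percentiles will be presented instead of mean, SD and 90% CI". The Synopsis repeats the rule. Neither place names the test or its significance level, or says whether it is applied per arm, per visit or to the pooled arms.

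Two other sections bear on this:

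- Section 19.1: "Summary statistics will be provided for all study variables with descriptive statistics". For numerical variables it lists the number of observations, mean, SD, median, minimum and maximum, with no condition attached. It does not mention a CI.
- Section 19.7: the change in the (redacted) quality-of-life measures "will be summarized with mean change, SD, and 90% CI", again with no normality condition.

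Section 16.3 describes CGI-I as a rating from 1 to 7. For the sample size, Section 19.9 says "there will be 30 mITT subjects in each group".

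**The concern.** The replacement rule withdraws the quantity that Section 19.3.3 defines as the endpoint. If the test rejects, the analyst cannot follow both sections: one requires a mean with a 90% CI, the other puts a median and two percentiles in its place. The replacement is also a different kind of summary. A 10th-to-90th percentile range describes the spread of individual ratings and does not shrink as the sample grows, and the rule provides no CI for the median.

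The trigger is open as well. A seven-category integer score cannot be normally distributed, so whether a test detects this depends on which test is used, at what level and on how many subjects. If the test is applied separately to each arm, one arm could be shown with a mean and CI and the other with a median and percentiles at the same visit.

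This matters because the study is an estimation pilot: its planned output is point estimates and 90% CIs by arm, to help plan a larger study. A planned interval for a named endpoint should not appear or disappear according to the data and a choice of test made later.

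**Working it through.** **Inputs from the protocol.** CGI-I takes integer values 1 to 7 (Section 16.3). The analysis n is 33 − 3 = 30 per arm (Section 19.9). The confidence level is 90% (Section 19.3.3).

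**The plan's own figures.** The plan gives no figure for CGI-I. Its only computed figures are the Wilson intervals at n = 30. They reproduce and are not in dispute: 18/30 gives 45.06% to 73.29%, half-width 14.11%; 8/30 gives 15.73% to 41.46%, half-width 12.86%.

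**Assumptions.** The documents contain no CGI-I data, so the score distributions below are assumed. Probabilities for scores 1 to 7:

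- A: .01, .04, .22, .46, .22, .04, .01
- B: .05, .20, .30, .30, .10, .04, .01
- C: .20, .35, .22, .15, .05, .02, .01
- D: .08, .17, .20, .25, .15, .10, .05
- E: .01, .05, .15, .60, .13, .05, .01

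Their SDs run from 0.93 (E) to 1.59 (D). For example, D has mean 3.72 and mean square 16.36, so its SD is √(16.36 − 3.72²) = 1.59. I used 4,000 simulated samples of n = 30 for each, and 2,000 for n = 60.

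**Step 1: how often the switch fires (% of samples).**

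| Test | A | B | C | D | E |
|---|---|---|---|---|---|
| Shapiro-Wilk 5%, n = 30 | 97.8 | 80.4 | 99.5 | 51.0 | 99.6 |
| Shapiro-Wilk 1%, n = 30 | 80.3 | 39.7 | 84.3 | 11.9 | 95.7 |
| Anderson-Darling 5%, n = 30 | 100 | 97.6 | 99.9 | 67.9 | 100 |
| D'Agostino K2 5%, n = 30 | 18.6 | 7.5 | 31.3 | 3.3 | 36.5 |
| Shapiro-Wilk 5%, n = 60 | 100 | 100 | 100 | 100 | 100 |

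The n = 60 row represents pooled arms that share one distribution. As a calibration check on truly normal data at n = 30, Shapiro-Wilk rejects in 4.6% and K2 in 5.3%, close to the nominal 5%.

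A second set of assumptions gives the same pattern. With normals rounded to 1–7 (mean 2.5 to 4, SD 1.0 to 1.6, n = 30, 5% level), Shapiro-Wilk rejects in about 85% to 99.5%, Lilliefors in 80% to 99.5%, Anderson-Darling in 92% to 100%, and D'Agostino-Pearson in 3% to 11%.

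**Step 2: mixed displays if applied per arm.** If both arms share a distribution and each rejects independently with probability p, the chance that exactly one arm switches is 2p(1 − p). With Shapiro-Wilk at 5%, this is 2 × 0.510 × 0.490 = 50% for D and 2 × 0.804 × 0.196 = 32% for B, at each visit.

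**Step 3: what replaces the CI.** The 90% t-interval is mean ± 1.699 × SD/√30, so its width is 2 × 1.699 × SD/5.477 = 0.620 × SD. That is 0.620 × 0.93 = 0.58 points for E and 0.620 × 1.59 = 0.99 points for D. The simulated average widths run from 0.57 to 0.98 points, while the 10th-to-90th percentile span averages 2.0 to 4.0 points. The two cannot be read interchangeably.

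**Step 4: whether the switch protects against a poor interval.** Coverage of the nominal 90% t-interval, in %:

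| | A | B | C | D | E |
|---|---|---|---|---|---|
| All samples | 90.1 | 90.0 | 89.0 | 89.9 | 89.9 |
| Samples where Shapiro-Wilk 5% rejects | 90.1 | 88.5 | 89.4 | 87.3 | 89.8 |

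The interval that the rule would suppress performs close to nominal, even in the samples where it would be suppressed.

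**The case against.** The strongest reply is that little information is lost. If Section 19.1 is honoured, n, mean and SD are reported in any case, and a reader can compute the 90% CI from them. CGI-I is a descriptive secondary endpoint in a pilot with no planned between-arm test, and no decision rests on it. A default followed by a stated exception is an ordinary structure for a plan. The test and its level may be named in the separate SAP, to which Sections 19.1 and 19.5 defer and whose text is not available. Medians and percentiles are a defensible summary of an ordinal rating. The firing rates rest on invented distributions and run from 3% to 100%.

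Much of this stands, and it limits the point. The consequence is small and the rates are illustrative. The exploratory endpoints and the quality-of-life measures are redacted, so it cannot be settled whether the rule reaches those in Section 19.7; that section shows a difference in approach, not a proven contradiction.

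Three things remain. Naming the test in a SAP would not cure the clash: after a rejection, Section 19.5 still withdraws what Section 19.3.3 defines. Section 19.1 does not promise the CI, and the text does not say whether the replacement rule overrides Section 19.1. The value of a median and percentiles as a summary is a reason to add them, not to drop the planned estimate and its interval.

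**Conclusion.** The concern holds. As written, the plan can remove the CGI-I mean and 90% CI that define a secondary endpoint and leave no interval estimate, on the result of a test whose name, level and unit of application the protocol does not give. This follows from the text alone.

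The frequency depends on assumptions about the scores and the test. At n = 30 and the 5% level, the five assumed distributions give 51% to 99.6% for Shapiro-Wilk and 3% to 37% for D'Agostino K2. The safe conclusion is that the choice of test largely decides whether the endpoint is shown. Nothing is gained in return, since the ordinary interval covers 89.0% to 90.1% overall and 87% to 90% after a Shapiro-Wilk rejection at 5%.

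The point should be corrected but does not threaten the study's main result. It concerns CGI-I and any exploratory change scores the rule covers. The EDSS and MSIS-29 responder rates are proportions with Wilson intervals, to which a normality test cannot sensibly apply, although the sentence nominally covers all efficacy endpoints.

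**What to change.** In Section 19.5 and the matching Synopsis paragraph, either delete the normality rule or change *instead of* to *in addition to*. The mean, SD and 90% CI are then always reported for CGI-I and the exploratory change scores, which agrees with Sections 19.3.3 and 19.1 and with the approach in Section 19.7. The median, the 10th and 90th percentiles and the CGI-I category counts can be shown alongside as supplements. With the condition gone, no normality test needs to be specified.

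The cost is a wording change in two places and slightly larger tables. No new data are needed.
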